## 9.9 Data Monitoring

All aspects of the study will be monitored by qualified individuals designated by the sponsor. Monitoring will be conducted according to Good Clinical Practice and applicable government regulations. The investigator agrees to allow monitors access to the clinical supplies, dispensing and storage areas, and to the clinical files of the study subjects, and, if requested, agrees to assist the monitors.

Safety monitoring will include careful assessment and appropriate reporting of adverse events. Medical monitoring will include contemporaneous assessment of serious adverse events.

The monitoring of subject safety and data quality will follow the NINDS Guidelines for Data and Safety Monitoring in Clinical Trials. A Data and Safety Monitoring Board (DSMB) appointed by the NIH/NINDS will meet at six-month intervals (or as determined by the NINDS) to review partially unblinded study data provided by the study statistician. This committee will monitor rates of adverse events and endpoints in the trial and will monitor the performance of the trial. The frequency and format of DSMB meetings, reports, and guidelines for interim analysis will be agreed upon prior to study subject enrollment.

The Protocol PI will appoint an Independent Medical Monitor (IMM) to review all adverse events, in a blinded fashion, on a periodic basis. In addition, the IMM will review all events that meet the regulatory definition of a Serious Adverse Event, upon receipt of notification via the Electronic Data Capture (EDC) system.

An adverse event (AE) is any unfavorable and unintended sign (including a clinically significant abnormal laboratory finding, for example), symptom, or disease temporally associated with a study, use of a drug product or device whether or not considered related to the drug product or device. FDA, Office of Human Research Protection (OHRP), and NeuroNEXT CIRB requirements for reporting AEs will be followed. Subjects will be monitored for AEs from the time they sign consent until 30 days following permanent discontinuation of study drug. At that point, all ongoing AEs will be followed to resolution, but no new AEs will be recorded. The IMM/DSMB will review cumulative AEs; the frequency of this review will be determined by the IMM/DSMB in conjunction with the Protocol PI.

Subjects will be monitored for AEs from the time they sign consent until the final Study visit. If an AE is ongoing or discovered at a subject's final Study visit, the AE will be followed until resolution, or for a minimum of 30 days, whichever comes first. Resolution means that the subject has returned to status at enrollment. If the AE is still ongoing after 30 days, it will be resolved with sequelae. All AEs monitored past the final visit can be followed via telephone – a repeat Termination/Final Follow-up visit does not need to occur.

All SAEs must be followed until resolution throughout the trial. SAEs that are discovered less than 60 days prior to the subject's final Study visit will be followed until resolution or for a minimum of 60 days, whichever comes first, even if it is past the final visit. If a new SAE is discovered at the subject's final Study visit, it must be followed until resolution, or for a minimum of 60 days, whichever comes first. If the SAE is still ongoing after 60 days, it will be resolved with sequelae. All SAEs monitored past the final visit can be followed via telephone – a repeat Termination/Final Follow-up visit does not need to occur.

Each Clinical Study Site Investigator and research team (co-Investigators, research nurse, clinical trial coordinator) are responsible for identifying and reporting AEs and determining the relationship of the event to the study drug. Aggregate reports blinded by treatment group, detailed by severity, attribution (expected or unexpected), and relationship to the study drug, will be available from the DCC for review by the IMM. A separate report detailing protocol compliance will also be available monthly from the DCC for review by the Protocol PI, who will provide feedback to individual sites as needed. The Protocol Steering Committee (PSC) will advise the Protocol PI as to whether the protocol or informed consent document requires revision based on these reports.

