## **6.2.3 Study Medication/Intervention Discontinuation Evaluations/procedures**

Study medication/intervention discontinuation will occur when subjects complete the study or withdraw from the study early (after randomization). At study completion, subjects will complete all the assessments and procedures for the 16 month visit (visit 14).

If a subject withdraws from the study after randomization, a Termination visit should be conducted as soon as possible. The assessments and procedures completed during the termination visit will depend upon whether the subject discontinued study drug prior to the termination visit. Assessments and procedures are to be completed as possible based on agreement of the caregiver at the termination visit(s) as follows:

- The subject is on study drug at the time of the visit
  - The termination visit will include all the assessments and procedures for the 16 month visit (visit 14).
- The subject discontinued study drug prior to the visit
  - The termination visit will include the following safety assessments and procedures
    - Blood draw
    - Urine dipstick
    - EKG
    - Vitals
    - Physical, neurological and psychological exams
    - Suicidality assessment
    - Fundoscopic exam

- AE review
- Study drug accountability

A follow up visit after the Termination Visit with the subject off study drug should be conducted 30 days after the termination visit.

Study medication will be weaned over 1-2 weeks for subjects on a dose of >25 mg BID AFQ056 or placebo, and stopped without weaning for subjects on a dose of 12.5 or 25 mg BID. For participants on a dose of 50 mg BID, the dose will be weaned to 25 mg BID for a week and then stopped. For participants on 75 mg BID or 100 mg BID, the dose will be weaned to 50 mg BID for a week and then to 25 mg for a week, and then stopped.

Discontinuation criteria for individual subjects are listed in section 4.3 of the protocol – please refer to that section for more details.

The entire trial will be stopped if 3 serious adverse events considered probably or definitely due to drug occur or upon recommendation by the DSMB based on unblinded review of adverse events.

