#### **6.2.5 Final On-Study Evaluations**

All subjects will complete the Follow Up visit (visit 15) as the final visit of the study. At that time, subjects will be off of study medication and will turn in all empty bottles of study medication. Parents/caregivers of subject will be instructed to call the site Investigator or study staff should there be any concerns after the follow up visit. Subjects may continue to receive the language intervention indefinitely as delivered by the parent, but this will no longer be monitored by the language therapist. Please refer to the SOA for the complete list of procedures and assessments done at this visit.

If a subject withdraws from the study after randomization and stops taking study drug prior to the termination visit (Month 16, Visit 14), the follow up visit (visit 15) will consist of a phone call or email to check for adverse events that will occur 30 days after the termination visit.

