Subjects will be monitored for AEs from the time they sign consent until the final Study visit. If an AE is ongoing or discovered at a subject's final Study visit, the AE will be followed until resolution, or for a minimum of 30 days, whichever comes first. Resolution means that the subject has returned to status at enrollment. If the AE is still ongoing after 30 days, it will be resolved with sequelae. All AEs monitored past the final visit can be followed via telephone – a repeat Termination/Final Follow-up visit does not need to occur.

All SAEs must be followed until resolution throughout the trial. SAEs that are discovered less than 60 days prior to the subject's final Study visit will be followed until resolution or for a minimum of 60 days, whichever comes first, even if it is past the final visit. If a new SAE is discovered at the subject's final Study visit, it must be followed until resolution, or for a minimum of 60 days, whichever comes first. If the SAE is still ongoing after 60 days, it will be resolved with sequelae. All SAEs monitored past the final visit can be followed via telephone – a repeat Termination/Final Follow-up visit does not need to occur.

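### Section 9.9 gives two incompatible rules for ending adverse-event collection and follow-up; the one repeated elsewhere closes ongoing events as resolved with sequelae, against its own definition of resolution

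*Combined protocol and SAP*

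**What the plan says.** Section 9.9 first ties the end of collection to the drug: "Subjects will be monitored for AEs from the time they sign consent until 30 days following permanent discontinuation of study drug". It continues: "At that point, all ongoing AEs will be followed to resolution, but no new AEs will be recorded". That rule sets no time limit on following an ongoing event.

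The next paragraph of section 9.9 ties the end of collection to a visit. The same text stands in sections 8, 10.4 and 10.4.1.3: "Subjects will be monitored for AEs from the time they sign consent until the final Study visit". An event that is ongoing or found at that visit is followed until it resolves or for a stated minimum of 30 days, whichever is first. Then: "If the AE is still ongoing after 30 days, it will be resolved with sequelae". Serious events have the same construction at 60 days: "If the SAE is still ongoing after 60 days, it will be resolved with sequelae". The paragraph also gives its own definition: "Resolution means that the subject has returned to status at enrollment".

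Section 6.2.5 identifies the final visit: "All subjects will complete the Follow Up visit (visit 15) as the final visit of the study". Nothing in the document says which of the two rules governs.

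**The concern.** The two rules differ on two matters. The first is when new events stop being collected. Weaning takes place between visit 14 and visit 15 and lasts longer at higher doses, so a cut-off fixed to visit 15 leaves less time off drug as the dose rises. A cut-off fixed to the last dose does not.

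The second is what happens to an event that has not ended. One rule keeps it open. The other closes it under an outcome beginning with the word resolved, although the child has by definition not returned to enrolment status. Combining a minimum of 30 days with a whichever-is-first clause also turns that minimum into a maximum.

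Long-term safety is a stated objective (section 1.3.1) and one of the reasons given for the extension (section 2.1). Visit 15 is meant in part to show changes after coming off drug (sections 9.1 and 9.6.3). If sites apply different rules, capture after stopping and recorded outcomes will vary for reasons unrelated to the children.

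**Working it through.** No figure in the plan needs reproducing; the check is calendar arithmetic followed by a comparison of the texts.

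**Inputs**
- Visit 15 is one month after visit 14 (section 9.1), taken as 30 days. Schedule check: 4 + 8 + 8 + 1 = 21 months, the total given in the Synopsis.
- Weaning follows visit 14. Section 6.3.14 holds the dose stable through visit 14 and dispenses drug there to cover weaning; section 9.6.3 treats visit 14 as the last visit before weaning.
- Wean length (section 6.2.3): 14 days at the top two doses ("For participants on 75 mg BID or 100 mg BID, the dose will be weaned to 50 mg BID for a week", followed by a second week at 25 mg), 7 days at 50 mg BID, none at 12.5 or 25 mg BID.
- Each visit may move 5 days either way around a date set from visit 3 (sections 6.1 and 6.2), so the gap between visits 14 and 15 can vary by 10 days either way.

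**Formulas**
- Days off drug at visit 15 = 30 − wean length; range = (20 to 40) − wean length.
- Shortfall against the 30-day rule = 30 − days off drug at visit 15, which equals the wean length.
- Closure of an event ongoing at visit 15, in days after the last dose = days off drug + 30. For a serious event discovered at visit 15 it is days off drug + 60.

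| Dose | Wean | Days off drug at visit 15 (range) | Shortfall | Event closed, day | Serious event closed, day |
|---|---|---|---|---|---|
| 75-100 mg BID | 14 | 30 − 14 = 16 (6 to 26) | 14 | 16 + 30 = 46 | 16 + 60 = 76 |
| 50 mg BID | 7 | 30 − 7 = 23 (13 to 33) | 7 | 23 + 30 = 53 | 23 + 60 = 83 |
| 25 mg BID or less | 0 | 30 − 0 = 30 (20 to 40) | 0 | 30 + 30 = 60 | 30 + 60 = 90 |

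A month of 30.4 days adds 0.4 day to the off-drug and closure figures and takes 0.4 day off each shortfall.

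**The ongoing event.** Take an event at 100 mg BID that is present at visit 15 and still present 30 days later. Under the first rule it stays open until it resolves. Under the second it is closed at about day 46 as resolved with sequelae. Under the definition in that same paragraph it has not resolved. The result is the same at every dose; only the day changes. The adverse event form described in section 6.3.9 already records whether a problem is ongoing, so an accurate entry is possible.

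**The case against.** Several stronger readings are tempting, and the documents do not support them.

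- A reader might infer that events are closed about 16 days after the last dose. They are not. Day 16 is when collection of new events ends at 75-100 mg BID; an event ongoing then is followed for a further 30 days.
- A reader might infer that a child whose visit 15 is missed after an on-drug termination visit has no off-drug observation at all. Section 6.2.3 calls for an off-drug follow-up 30 days after the termination visit. Section 4.3 provides for contact by phone or email, though its list layout leaves the scope unclear, and section 6.2.5 provides it where drug stopped before the termination visit. For shortened extensions, the Synopsis has treatment including weaning end before 31 August 2021, and section 6.1 places the termination visit by that date. The order of the two is not stated, so that visit may follow the wean.
- A reader might infer that planned tables will understate unresolved harm. Section 9.7 tabulates and compares frequencies; no analysis by outcome is specified. For children who complete the blinded phase, visit 15 falls at month 17, nine months after the randomised comparison ends at month 8.

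Other points also weigh against a large effect. All completers are observed for about the same month after visit 14, and the first dose reduction falls inside it. The stated adult half-life is 8 to 9 hours (section 2.2), so five half-lives take 40 to 45 hours and residual exposure is not the issue. Learning and memory are monitored through test scores (section 7), which section 10.4.1.1 keeps out of adverse event recording. Retinal change is checked by funduscopy at visit 15 (section 6.3.9). The phrase with sequelae does signal incomplete recovery. The 6-day lower limit needs visit 14 five days late and visit 15 five days early.

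These points limit the consequences. None reconciles the two rules or makes an ongoing event a resolved one.

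**Conclusion.** The contradiction is real and needs correcting. For scheduled completers who wean after visit 14, the two end dates for collecting new events differ nominally by 14 days at 75-100 mg BID, 7 days at 50 mg BID and 0 days at 25 mg BID or less. The conflict over ongoing events, and the outcome label that contradicts the stated definition, apply at every dose and to serious events as well.

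The effect is on capture of late or withdrawal-related events after stopping drug, and on outcome records kept for the long-term safety objective. The randomised 8-month frequency comparison and the primary efficacy inference are not affected.

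The day counts assume a 30-day month, weaning that starts at visit 14, and visits on their nominal dates. They do not apply to children who stop drug before a termination visit. For shortened extensions the interval cannot be fixed from the text. The number of events concerned cannot be estimated from the documents.

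**What to change.** State one collection and follow-up rule, word it identically in sections 8, 9.9, 10.4 and 10.4.1.3, and anchor it to the recorded date of the last dose. The documents do not show which rule was intended, so the choice is the sponsor's. If the 30-day window after discontinuation is kept, add a phone or email contact for adverse events when visit 15 falls less than 30 days after the last dose or is missed. This is consistent with contacts already provided for in sections 4.3, 6.2.3 and 6.2.5.

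Whichever rule is kept, replace the closing instruction for events still present at a follow-up limit (30 days, or 60 for serious events) with *outcome recorded as not resolved/ongoing at last contact*. Reserve resolved with sequelae for events that have actually ended.

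The cost is amendment wording, one outcome code on the adverse event form and, if the 30-day window is kept, one short contact for children weaned from 50-100 mg BID or without visit 15. No dose, weaning step or scheduled visit changes.

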## **10 DATA COLLECTION, SITE MONITORING, AND ADVERSE EXPERIENCE REPORTING**

### **10.1 Data Management**

Site personnel will collect, transcribe, correct, and transmit the data onto source documents, CRFs, and other forms used to report, track and record clinical research data. The DCC will monitor clinical sites to ensure compliance with data management requirements and Good Clinical Practices. The DCC is responsible for developing, testing, and managing clinical data management activities, as required, at the study sites, the CCC, and at the DCC.

The general NINDS Common Data Elements (CDE) will be used to construct data collection forms. All study data will be collected via systems created in collaboration with the DCC and will comply with all applicable guidelines regarding patient confidentiality and data integrity.

### **10.1.1 Registration**

Registration of participants on this protocol will employ an interactive data system in which the clinical study site will attest to the participant's eligibility as per protocol criteria and obtain appropriate informed consent. NeuroNEXT CIRB approval for the protocol must be on file at the DCC before accrual can occur from the clinical study site.

The DCC will use a system of coded identifiers to protect participant confidentiality. When the participant is registered to participate in the study using the DCC-provided web-based registration, the system will assign a participant ID number. The unique ID code will include a site ID, and a unique participant ID. To confirm the correct participant ID, the data entry system will require a second entry of the unique participant ID and compare for consistency. In this fashion, no personal identifiers would be accessible to the DCC and the data will be collected on the correctly identified subject.

### **10.1.2 Data Entry**

Data entry will occur at the enrolling clinical study sites. Data quality assurance and analyses will be performed by the DCC. The DCC, located at the University of Iowa, will coordinate all data and statistical services for the study, as well as on-site monitoring for all participating clinical study sites.

Data collection for this study will be accomplished with online electronic case report forms. Using encrypted communication links, online forms will be developed that contain the requisite data fields.

## **10.2 Role of Data Management**

Data Management (DM) is the development, execution and supervision of plans, policies, programs, and practices that control, protect, deliver, and enhance the value of data and information assets.

All data will be managed in compliance with NeuroNEXT policies, and applicable Sponsor and regulatory requirements. The DCC will instruct site personnel to collect, transcribe, correct, and transmit the data onto source documents, CRFs, and other forms used to report, track and record clinical research data. The DCC will monitor clinical sites to ensure compliance with data management requirements and Good Clinical Practices. The DCC is responsible for developing, testing, and managing clinical data management activities, as required, at the clinical study sites (CSS), the CCC, and at the DCC.

The DCC is responsible for all aspects of clinical data management, and for properly instructing key study personnel (including the CCC, the CSS, and DCC staff) on how to collect, transcribe, correct and transmit the data onto CRFs or other data collection forms and logs.

The DCC is responsible for establishing procedures to ensure that clinical data management activities occur as required at the CCC, the CSS, and at the DCC.

## **10.3 Quality Assurance**

By signing this protocol, the Sponsor and Investigator agree to be responsible for implementing and maintaining quality control and quality assurance systems with written standard operating procedures (SOPs) to ensure that studies are conducted and data are generated, documented,

and reported in compliance with the protocol, accepted standards of GCP, and all applicable federal, state, and local laws, rules and regulations relating to the conduct of the clinical study.

#### **10.3.1 Development of Monitoring Plan**

Onsite and remote monitoring visits will be conducted by DCC monitors according to a pre-defined Monitoring Plan. The monitoring plan will detail the frequency of on-site visits and remote review of source documentation and CRFs, the study data to be monitored, the review of any regulatory files, drug and supplies accountability (if applicable), documentation of remote reviews and on-site visit, and the resolution process for data errors that are discovered during visits and remote reviews. All participating clinical study sites will be monitored at least once after a study initiation visit and all sites will have a close-out visit for each protocol. Two remote reviews are anticipated for each clinical study site per year. All subjects will be monitored for inclusion and exclusion criteria, informed consent procedures, and adverse events. A certain percentage of data is also monitored/ source data verified against the data entered into the study database. The monitoring plan will include flexibility to revise the frequency of visits/remote reviews, or data monitored depending on clinical study site or study related issues.

#### **10.3.2 Site Monitoring Visits**

On-site monitoring visits will be conducted by DCC monitors according to a pre-defined monitoring plan for each protocol. The goal of on-site monitoring is to analyze (review) the data as it is collected, to check the validity and integrity of the data, to verify source documentation, to ensure protection of human subjects, and to ensure protocol compliance with federal regulations. During the monitoring visit, the monitor assesses the overall status of the study, staff, and facilities to determine whether the study is being conducted per protocol and in compliance with regulatory requirements. The monitor also conducts a CRF review that includes checks of all adverse event documentation, verifies the presence of all critical correspondence and records related to investigational products and clinical supplies (if applicable), and determines if protocol violations have occurred and are documented properly. After the monitoring visit, the monitor documents the results of the monitoring visit and completes a post-visit monitoring letter that conveys any issues discovered during the visit and the need for data corrections, if appropriate. Drug and supplies accountability may also be monitored during the site visit. The DCC will work closely with the CCC to monitor and document drug distribution from the manufacturers to the clinical study sites (CSS). Each CSS will be provided with a drug accountability log which will be reviewed by the DCC monitors and reconciled with distribution logs. At the study closeout visit, the monitors confirm that appropriate data have been reviewed, source documentation has been verified, and all required documents are present in the Study Regulatory File.

